3. METHODS

3.1 Study design

Hip osteoarthritis patients eligible for THA and placed on the waiting list for surgery will be included when the preoperative intake questionnaire is completed between 1-4-2020 and 1-1-2022. In a retrospective dataset we compare two standard care strategies: THA and wait-and-see, in which patients did not receive THA and remain on the waiting list. Patients were assigned to one of the two groups based on

whether surgery could be performed or whether THA was cancelled and patients remained on the waiting list. The first group (THA group) consists of patients that received surgery before 1-1-2022 and completed a 3-months postoperative questionnaire before 1-4-2022. The second group (control group) consists of patients which did not receive surgery before 1-1-2022 and completed a waiting list questionnaire before 1-4-2022. The target trial and emulation plan are shown in Figure 1 and the time-schedule of the emulation trial is shown in Figure 2. Patients that received THA on both sides between 1-4-2020 and 1-1-2022 will be excluded. The response rates on follow-up questionnaires will be reported for both groups. We will compare characteristics (age, sex, PROM-outcomes at baseline and physical therapy before the hospital visit) for patients that completed the follow-up questionnaires (completers) and patients that did not complete the follow-up questionnaires (non-completers). In the primary analysis we will correct for patient characteristics.

Target trial → Emulation

[figure not shown]
[figure not shown]

Figure 2: Timeline target trial emulation

THA= Total Hip Arthroplasty

FU = Follow-up

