In this study we compare the effect of THA compared to non-surgery on hip disability measured with the HOOS-PS change score from baseline up to approximately 3-months by means of RCT Target Trial Emulation, which aims to mimic a traditional RCT. Function and pain as a secondary outcome are measured by means of patient reported outcome measures (PROMs) pre-operatively and post-operatively or post-waiting list. The pre-operative intake questionnaire and the 3-months postoperative questionnaire are part of standard care. The waiting list questionnaire was administered during the Covid-19 pandemic to monitor patients' health status in two Santeon Hospitals (OLVG and Martini) in all patients who were at least three months on the waiting list. Therefore our study will be performed with data of these two Santeon Hospitals. All data is available through the routinely collected data for hip osteoarthritis within the VBHC program and in addition the outcomes of the administered waiting list questionnaire. Therefore, it is not needed to obtain additional information from patients.

To test the assumption that group allocation is (pseudo)random and cannot be explained by patient characteristics or severity of pain and hip disability at baseline, a logistic regression analysis will be performed on patients within the VBHC data set between 1-4-2020 and 1-1-2022. Group being the dependent variable (THA vs. non-surgery) and age (continuous), sex (M/F), physical therapy before the hospital visit (yes/no), follow-up time in days (continuous), pain at baseline (NRS, continuous) and the HOOS-PS at baseline (continuous) will be included in the model as independent variables. Secondly, we will test the assumption that follow-up time in days is not statistically significantly different between the THA and non-surgery group. Follow-up time is defined by calculating the number of days between the date of the orthopedic visit) and the date of the follow-up questionnaire. Results will be considered statistically significant when $p \leq 0.05$. In case an independent variable has a statistically significant effect on group assignment and/or follow-up time in days is significantly different between the two groups, clinical relevance will be considered and discussed within the research team, for example the effect size on chance to be allocated to the THA or non-surgery group.

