1.2 Recruitment and selection of subjects

1.2.1 Screening/selection

Retrospective data will be collected by [name] and the VBHC data analysts at OLVG and Martini hospital.

1.2.2 Study population
 
Patients with hip osteoarthritis that were on the waiting list for THA between 1-4-2020 and 1-1-2022 and had a completed intake questionnaire will be included. The number of patients is dependent on how many patients completed the questionnaires and needs to be investigated. However, based on the waiting list at the time and the number of performed surgeries in the two hospitals, we expect to include at least 100 patients in each cohort (THA group and non-surgery group). Since we use observational data for trial emulation, no sample size calculation is needed (8).

1.2.3 Inclusion criteria
 
Inclusion criteria:
 
 - Patients on the waiting list for primary THA between 1-4-2020 up to 31-3-2022 in OLVG or Martini hospital. - Completed intake questionnaire (HOOS-PS baseline) - Indication osteoarthritis of the hip

1.2.4 Exclusion criteria
 
Exclusion criteria:
 
 - Patients that received THA on both sides within follow-up (1-4-2020 and 1-1-2022) will be excluded. - Patients with other indications than osteoarthritis of the hip were excluded.

1.2.5 Number of subjects/ sample size
 
Since we use observational data for trial emulation no sample size calculation is needed (8). The participants are already exposed to an intervention or not. Differences in the primary and secondary outcomes (PROMs) between groups will be interpreted using 95% confidence intervals and thresholds for clinical relevance which are reported below.

1.3 Data collection: variables and measurement methods
 
1.3.1 Primary outcome measure (dependent variable)
 
Primary outcome is the change score for hip function measured with the HOOS-PS at 3-months postoperative in the THA group and at least 3-months post waiting list in the control group compared to baseline. The HOOS-PS is a 5-item questionnaire that quantifies hip disability. The raw outcome is converted to a Rasch-based interval score ranging from no difficulty (0) to extreme difficulty (100) (3,4,5). The minimal clinically important difference (MCID) for the HOOS-PS is 23 points (6). We will also calculate the minimal important change in our study population, based on an anchor question.

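### A control keeps an outcome only after at least three months on the waiting list, a THA patient whatever the wait; a sensitivity analysis should apply the same condition to both groups

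*Combined protocol and SAP*

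**What the plan says.** All references are to the combined protocol and SAP.

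- **Eligibility (1.2.3 Inclusion criteria).** One list serves both groups: "Patients on the waiting list for primary THA between 1-4-2020 up to 31-3-2022 in OLVG or Martini hospital", a completed intake HOOS-PS and an osteoarthritis indication. No minimum wait is set for either group.
- **THA group (3.1 Study design).** It consists of "patients that received surgery before 1-1-2022 and completed a 3-months postoperative questionnaire before 1-4-2022".
- **Control group (3.1).** It consists of "patients which did not receive surgery before 1-1-2022 and completed a waiting list questionnaire before 1-4-2022". That questionnaire was administered in two hospitals "in all patients who were at least three months on the waiting list".
- **Outcome timing (1.3.1 Primary outcome measure).** THA patients are measured at three months after surgery. Controls are measured "at least 3-months post waiting list in the control group compared to baseline".
- **Models (3.1 and 1.4.2 Analyses).** The outcome regressions and the logistic check on allocation both include follow-up time, defined as the "number of days between the date of the orthopedic visit) and the date of the follow-up questionnaire". The wait before surgery is not a separate term. The order date and surgery date are both in the variable table (1.3.2).

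**The concern.** In the trial being emulated, every patient assigned to non-surgery would count from time zero, including those who improved, withdrew or deteriorated in the first weeks. Here a listed patient operated on at week 4 is kept in the THA group, while a listed patient who leaves the list unoperated at week 4 is in neither group. Only the control mean is therefore conditional on still being listed at three months. If those who leave differ in prognosis from those who stay, the control mean is shifted and the estimated THA effect moves with it.

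The planned checks do not reach this. The logistic regression compares patients who have already been sorted into groups. Comparing completers with non-completers at baseline does not separate patients who left the list early, and so were never due the form, from patients who were sent it and did not reply. What is at stake is the causal claim in the closing paragraph of 3.1, and the population to which it applies.

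**Working it through.** The plan has no figure to reproduce. Section 1.2.2 expects at least 100 patients per group, and 1.2.5 says no sample size calculation is needed. No SD, wait distribution or rate of leaving the list is given. Every number below other than the 100, the 23 points and the calendar dates is an assumption or follows from one.

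**1. Where each listed patient ends up, by the definitions in 3.1** (given that the required form is completed)

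| Course after intake | Group |
|---|---|
| Operated within three months of listing, before 1-1-2022 | THA |
| Still waiting at three months, operated later but before 1-1-2022 | THA |
| Still waiting at three months, not operated before 1-1-2022 | Control |
| Leaves the list unoperated before three months | Neither |

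The last row is the gap: it removes patients from the non-surgery side only.

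**2. Size of the shift from early leaving**

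Let a share s of would-be controls leave early, with a mean change differing by d points from that of stayers. The mean over all would-be controls is (1 − s) × stayers + s × (stayers + d) = stayers + s × d. The observed control mean uses stayers only, so it is off by s × d.

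- s = 5%, d = 15: 0.05 × 15 = 0.75 points
- s = 10%, d = 20: 0.10 × 20 = 2.0 points

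Against the 23-point MCID, 2.0/23 is 8.7%. The sign follows the sign of d, which the documents do not give.

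**3. How many THA patients would fail the same three-month condition**

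Simulation: uniform intake over 21 months (1-4-2020 to 1-1-2022), surgery before the end of that window, two assumed shapes for the wait.

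| Mean wait (months) | Wait under 3 months, exponential | Wait under 3 months, gamma (shape 4) |
|---|---|---|
| 3 | 69% | 60% |
| 6 | 51% | 18% |
| 9 | 43% | 7% |

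The range of 7% to 69% shows that this share cannot be judged without the data. It measures how far the restriction would bite; it is not a measure of bias.

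**4. Precision after restricting the THA group**

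The unadjusted 95% half-width is 1.96 × SD × √(1/100 + 1/n), with 100 controls and an assumed SD of 20.

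- n = 100: 5.5 points
- n = 57 (43% removed): 6.5 points
- n = 31 (69% removed): 8.1 points

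**5. Effect of the restriction on follow-up**

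THA follow-up is roughly the wait plus three months. Under exponential waits with means of 3, 6 and 9 months, mean THA follow-up rises from 5.5, 7.0 and 7.7 months to 8.4, 9.7 and 10.3 months.

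**The case against.** The best case against the point is that a control outcome at three months or later necessarily requires three unoperated months, so the condition is a matter of when the outcome is measured rather than who is eligible. Much of that stands, and it rules out three stronger readings that a reader might infer.

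- **That the groups have different eligibility.** They do not. The written criteria and the intake baseline are the same; the difference is in who is retained with an outcome. THA patients also pass a post-baseline condition of their own, surgery and a reply three months later, and some of them will have waited more than three months.
- **That short-wait THA patients have no counterpart among controls.** Had their surgery been cancelled, they could have stayed listed, reached three months and received the form. A short wait is part of getting THA, not a baseline trait that needs a match.
- **That the THA effect is overstated.** This holds only if early leavers did better than stayers. Patients may also leave because of worsening health, death or surgery elsewhere, which could reverse the sign. The documents report no rate or reason.

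It can also be said that follow-up time in the models carries the wait. For THA patients it partly does. However, it mixes the wait with outcome timing and does not apply the three-month condition to both groups. Early leavers with an intake form might appear among the non-completers, but the plan does not say that they will be identified or counted. The target-trial figure and the timeline were not available to this review and may say more about time zero; the text nevertheless defines both groups.

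**Conclusion.** The point holds as an asymmetry in retention after baseline. Controls are conditioned on being listed and unoperated at three months or later, THA patients have no matching condition, and no planned analysis applies one. Bias follows only if leaving the list or wait length is related to prognosis; under the plan's own assumption that timing was unrelated to the patient, the wait-length route would vanish.

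The early-leaving route is worth about 0.8 to 2 points in either direction, on assumed inputs of 5-10% leaving and a 15-20 point difference. That would not by itself overturn a conclusion well clear of 23 points, but it could matter for an estimate close to that threshold. The wait-length route is not sized here. The change is advisable because it is cheap and bears directly on the emulation claim; the point does not show that the primary estimate is wrong.

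**What to change.** Add a pre-specified sensitivity analysis to 1.4.2: run the same two regressions with the THA group restricted to patients whose surgery date is at least three months after the THA order date, and report it beside the primary estimate, with follow-up time by group. Also report how many listed patients with an intake form left the list unoperated before three months. State in advance that, if the two estimates differ materially, the conclusion is limited to patients who have waited at least three months. The primary analysis stays as planned.

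**Cost.** The rerun uses two dates already collected. The count of early leavers may need one more extract, because the variable table lists no date of leaving the list.

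**Downsides.** The THA group is smaller and the interval wider (about 6.5 to 8.1 points instead of 5.5, on the assumptions above). THA follow-up from the orthopedic visit is also longer, which may make follow-up less similar between groups. Baseline remains the intake score, since no three-month score is listed for THA patients while still waiting, so this is not a full landmark analysis and should not be described as one.

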1. INTRODUCTION

Total hip arthroplasty (THA) is one of the most frequently performed orthopedic surgeries. Studies show that THA is an effective treatment to reduce pain and to improve hip function and quality of life in patients with osteoarthritis of the hip. However, the effectiveness of THA has never been investigated by means of a randomized controlled trial (RCT), which is the gold standard to assess effectiveness of an intervention.

During the Covid-19 pandemic, elective orthopedic interventions were defined as not urgent and therefore cancelled. The National Institute for Public Health and the Environment (RIVM) estimated that in 2020 and 2021 in total 32,000 Quality-Adjusted Life Years (QALYs) were not realized due to postponing THA in patients with osteoarthritis of the hip in the Netherlands (9, 10). Better understanding of the treatment effect of THA, compared to non-surgery, could help improve prioritization of interventions.

The ideal research design to investigate effectiveness of THA would be to randomize patients between surgery and (delayed) non-surgery. Such an RCT is deemed unethical due to the effect size of THA shown in observational studies. It is considered unethical to withhold the patients who are allocated to the conservative treatment from the apparent benefits of THA. The required investments in time and money to perform an RCT and expected difficulty to include sufficient patients do not outweigh the benefits of measuring the effect of THA to demonstrate its urgency. Moreover, a potential benefit of research with observational data is, that it better reflects real-world data.

During Covid-19, there were different phases of hospital reduction and restoring of surgical capacity. During periods when surgeries were scaled down nationwide, only emergency surgeries for fractures, infections, and revisions were performed in the orthopedic department. However, our study specifically

focuses on elective primary total hip replacements for osteoarthritis, and during the research period, there was no prioritization based on the severity of symptoms within this osteoarthritis population.

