We hypothesize that patient characteristics (i.e. sex, age, severity of symptoms at baseline) do not affect group allocation and follow-up time is similar for THA and non-surgery patients. If this is true, the proposed Target Trial Emulation will provide the first evidence on the effectiveness of THA surgery in terms of causal inference.

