1.4.2 Analyses

 1. Measure if THA is effective to improve physical function in patients with osteoarthritis of the hip compared to non-surgery by means of RCT Target Trial Emulation. 2. Assessment to test the assumption that group allocation to the surgery group or non-surgery group cannot be explained by patient characteristics by means of logistic regression analysis. Secondly we test the assumption that follow-up time in days is similar between the two groups. 
1. Measure effect of THA: Two multiple regression analyses will be performed with the HOOS-PS and pain change score, respectively, as the dependent variable, and experimental condition (THA/ no-THA), age, sex, HOOS-PS score at baseline, pain score at baseline, physical therapy before baseline (yes/no) and follow-up time in days as independent variables. All regression coefficients and their 95% confidence intervals will be provided. Differences will be considered statistically significant when $p \leq 0.05$ and clinically relevant when differences exceed the MCID of 23 points for the HOOS-PS and 2 points for the NRS (6,7).
 
Descriptives on all independent variables will be presented and assessed by visual inspection of boxplots (for continuous variables) or tables (for categorical variables). These results will be provided for transparency purposes.
 
2. Test whether assumptions for target trial emulation are met. A logistic regression analysis will be performed on patients within the VBHC data set between 1-4-2020 and 1-1-2022 to check whether the group allocation cannot be explained by patient characteristics. Group being the dependent variable (THA vs. non-surgery) and age (continuous), sex (M/F), physical therapy before the hospital visit (yes/no), follow-up time in days (continuous), pain at baseline (NRS, continuous) and the HOOS-PS at baseline (continuous) will be included in the model as independent variables. Results will be considered statistically significant when $p \leq 0.05$. In case an independent variable has a statistically significant effect on the outcome, clinical relevance will be considered and discussed for the effect size on chance to be allocated to the THA or non-surgery group. Secondly, we will test the assumption that follow-up time in days is not statistically significantly different between the THA and non-surgery group. Follow-up time is defined by calculating the number of days between the date of the orthopedic visit) and the date of the follow-up questionnaire.

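### The allocation check contains no severity measured after intake, so it has little or no power to detect selection for surgery by worsening on the waiting list

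*Combined protocol and SAP*

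**What the plan says.** The Introduction states that, in the study period, "there was no prioritization based on the severity of symptoms within this osteoarthritis population". It also says that the pseudo-random comparison has to be verified by analysis and cannot be settled in advance.

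The verification is specified in 3.1 Study design, where the assumption under test is that allocation "cannot be explained by patient characteristics or severity of pain and hip disability at baseline", and repeated in 1.4.2 Analyses, where its purpose is "to check whether the group allocation cannot be explained by patient characteristics". Group is regressed on age, sex and "physical therapy before the hospital visit (yes/no), follow-up time in days (continuous), pain at baseline (NRS, continuous) and the HOOS-PS at baseline (continuous"), with significance at p ≤ 0.05. Follow-up time is also compared between the groups. Significant terms are to be discussed for clinical relevance.

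The last paragraph of 3.1 hypothesises that "patient characteristics (i.e. sex, age, severity of symptoms at baseline) do not affect group allocation" and that follow-up time is similar. If so, the emulation is to count as evidence in causal terms.

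The waiting-list questionnaire was sent, to monitor health status, "in all patients who were at least three months on the waiting list" (3.1). The variable table in 1.3.2 lists waiting-list HOOS-PS, waiting-list pain, the questionnaire date and the surgery date. The analyses use the waiting-list scores as the control group's follow-up outcome and not in the allocation check.

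**The concern.** The THA group is anyone operated before 1-1-2022, with intake from 1-4-2020 onwards. If symptoms influenced who was operated and when, the symptoms that mattered would be those during the wait. Intake scores may by then be many months old. A check limited to intake severity can therefore look clean while surgery followed deterioration.

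The primary regression adjusts for the same intake variables, so adjustment does not close the gap. If worsening patients left the list for surgery, the remaining controls are those who stayed stable, and their mean change is too favourable. The study judges relevance against a fixed 23-point HOOS-PS threshold and intends its estimate to inform prioritisation of care (Introduction; 4.1 Valorization), so both the size and the direction of such a bias matter.

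**Working it through.** **No figure to reproduce.** Section 1.2.5 states that no sample size calculation is needed. The specification settles the main point; the numbers below only illustrate its size.

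**Specification side by side**
- Severity terms in the check (3.1, 1.4.2): intake NRS pain and intake HOOS-PS. None is measured later, and time to surgery is not modelled.
- Longest gap between tested severity and surgery: 1-4-2020 to 31-12-2021, about 21 months.
- Conditions for the causal reading (3.1, last paragraph): baseline characteristics and similar follow-up time. Course on the list is not among them.

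**Shift in control change.** Assumptions, none in the documents: standardised worsening z ~ N(0,1), P(surgery) = expit(b + ln(OR)·z), half of patients operated, SD of on-list change 10-15 points. Shift = (mean z among the unoperated) × SD.
- OR 1.5: mean z = -0.195. -0.195 × 10 = -1.95; -0.195 × 15 = -2.9.
- OR 2: mean z = -0.31. -0.31 × 10 = -3.1; -0.31 × 15 = -4.65.

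Higher HOOS-PS means more difficulty, so a negative shift makes controls look too stable and tends to understate the benefit of THA. A separate simulation with SD 12 agrees: about -2.3 (OR 1.5), -3.7 (OR 2) and -5.3 (OR 3). Selection in the opposite direction reverses the sign.

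**Power of the planned check.** Simulation of 1000 runs per scenario, N = 200 (1.2.2 expects at least 100 per group). Logistic regression of group on intake HOOS-PS, pain, age, sex and physical therapy; follow-up time was omitted. The p-values are two-sided, since the plan does not state sidedness. The entries give how often the intake HOOS-PS term has p ≤ 0.05.

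| OR per SD of worsening | Worsening unrelated to intake | Correlation -0.4 with intake |
|---|---|---|
| 1 (no selection) | 5-6% | 4-6% |
| 1.5 | 6% | 14-16% |
| 2 | 5-6% | 28-30% |
| 3 | 4-6% | 49-52% |

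In the unrelated case, at least one of the five terms is significant in about 20-23% of runs whether or not there is selection, so scanning the whole model adds no information there.

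**Power of a test of on-list change.** Same simulation, worsening unrelated to intake, on-list change added to the logistic model, by share of the 200 patients with a usable score.

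| OR | All | Half | A quarter |
|---|---|---|---|
| 1.5 | 78% | 49% | 24% |
| 2 | 99% | 88% | 54% |

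This is a binary-outcome test and only a guide to the Cox model proposed below. The first column is a ceiling: patients operated before three months on the list have no score.

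**Why the score cannot simply join the planned logistic model.** Controls may complete the questionnaire up to 1-4-2022, after the 1-1-2022 date that fixes group membership. A score dated after that cannot predict group. The analysis must start at the questionnaire date, among patients still unoperated before the cut-off.

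**The case against.** The strongest reply is that nothing in the documents suggests that worsening patients were pulled forward. The Introduction denies prioritisation by symptom severity without limiting this to intake, and describes external causes such as policy changes and surgeon quarantine. A reader might infer from this point that such prioritisation occurred; the documents do not support that. But the Introduction also says the assumption needs analysis, and the planned analysis does not reach this part of it.

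Four further objections narrow the point:
- A reader might infer that the check cannot detect such selection at all, or that it looks at intake severity alone. Neither is right. It also covers age, sex, physical therapy and follow-up time, and it picks up part of the selection if worsening correlates with intake score.
- A reader might infer that the waiting-list data would fully test the assumption. They would not. Patients operated before three months have no score, and controls whose questionnaire came after 31-12-2021 contribute no time at risk. The documents do not say how many operated patients have a score, or that theirs will be extracted.
- Selection of worsening patients runs against the study's hypothesis, and 2-5 points is small beside the 23-point threshold. It would not manufacture a finding of benefit. This stands for that direction only; without a test the direction is unknown.
- Making the causal statement pass or fail on a test with partial coverage and unknown power would be too rigid. This also stands, and the fix is worded accordingly.

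**Conclusion.** The gap is real and limited. Neither the allocation check nor the intake-adjusted primary regression addresses selection for surgery by worsening on the list, yet the last paragraph of 3.1 draws a causal reading without it. The check's power against such selection is at chance level if worsening is unrelated to intake score. At an assumed correlation of -0.4 it is about 14-16% at OR 1.5 and 28-30% at OR 2. The corresponding shift in control change is about 2-5 HOOS-PS points for SD 10-15 and OR 1.5-2, tending to understate the benefit. The SDs, odds ratios, correlations and share with a score are all assumptions. The reading of the model specification is not. This is a cheap improvement that should be made. It does not show that the comparison is confounded.

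**What to change.** Add a landmark analysis to analysis 2 in 1.4.2, and mirror it in 3.1:
- **Population:** patients with a waiting-list questionnaire completed before 1-1-2022 while unoperated, including those operated later.
- **Model:** Cox model of time from questionnaire to surgery, censored at 31-12-2021. Predictors are change in HOOS-PS and in NRS pain since intake, adjusted for intake scores and questionnaire date.
- **Report:** hazard ratios with 95% CIs, the numbers of operated and control patients covered, and the number dropped because the questionnaire came after the cut-off.
- **State:** selection among patients operated before three months remains untested, and a null result must be read through its confidence interval.

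Amend the last paragraph of 3.1 so that the causal statement also takes this result into account. If worsening predicted surgery, report the likely direction and size of the bias and qualify the statement, weighing clinical relevance as 3.1 already does for other predictors of allocation. Do not label the effect confounded automatically.

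Cost: one extra model and extraction of waiting-list scores for patients operated later. Coverage is partial and power is unknown until the number with a usable score has been counted.
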